7.8 Safety Analysis

The analysis of safety endpoint variables will include assessments of AEs, vital signs, 12-lead ECGs, physical examinations, and clinical laboratory tests. All Safety assessments will be summarized and tabulated as appropriate and will be listed by participant as applicable. All safety analyses will be performed on Safety Analysis Set. No formal statistical analysis will be performed on safety outcomes.

Example: The following variables will be evaluated to assess the safety:

- Adverse Events
- Clinical Laboratory Data
- 12 Lead Electrocardiogram (12-Lead ECG)
- Vital Sign measurements
- Physical Examination

Adverse Events:

Adverse Events will be coded using (MedDRA version 24.0 or latest) AE coding system for purpose of summary tables. Adverse events will be summarized using frequency count and percentage by MedDRA SOC and PT.

“Treatment-emergent” will be defined as starting or worsening after the first dose of investigational product. If the start date is missing, the event is assumed to be treatment emergent.

All AEs and TEAEs during the study will be summarized for the respective treatment group. A participant experiencing the same AEs and TEAEs multiple times will be counted only once for that PT. Similarly, if a participant experience multiple AEs and TEAEs (preferred terms) within the same SOC then that participant will be counted only once for that SOC. When summarizing by severity or relationship, only event with highest severity / relationship will be counted. Adverse events will be dichotomized into related (definitely, probably, and possibly) and unrelated (unlikely and not related) All AEs will be listed in chronological order of the events occurred.

An overview of AE summary will be presented. It will include the following:

- AEs
- Serious AEs
- TEAEs
- Serious TEAEs
- Treatment related TEAEs
- Treatment related Serious TEAEs
- TEAEs leading to study discontinuation
- TEAEs leading to death

The incidence and frequency of AEs will be summarized by treatment according to SOC and PT.

Treatment-Emergent Adverse Events (TEAEs)

A summary of the frequency (number and percentage of participants) of TEAEs will be presented by SOC, PT.

TEAEs will be summarized by treatment, system organ class, preferred term, and severity (mild, moderate, severe and undesirable, life-threatening or disabling and death).

TEAEs will be summarized by treatment, system organ class, preferred term and relationship to the study treatment is recorded as related (definitely, probably, and possibly) and unrelated (unlikely and not related). The number (%) of participants having relationship for each event and the number of events will be presented.

All AEs (including non-TEAEs) recorded on the CRF will be listed.

Adverse Events of Special Interest

A summary of the frequency (number and percentage of participants) of AESIs will be presented by SOC, PT and Listed separately.

Serious Adverse Events

SAEs and treatment related SAEs will be summarized separately by SOC and PT. All SAEs recorded on the CRF will be listed for all participants.

Adverse Events Leading to Study Drug Discontinuation

All AEs leading to discontinuation recorded on the CRF will be listed.

Deaths

Deaths occurring in the study will be listed for all participants.

Clinical Laboratory Data

The Clinical Laboratory test category will include the following assessments:

Hematology: Hemoglobin, Hematocrit, Red blood cells count, white blood cell count, red cell indices, Platelet count and differential (neutrophil, lymphocyte, monocyte, eosinophil, and basophil). Visits include screening, Day 0, Day 7, Day 56.

Biochemistry: Sodium, Total protein, Total and indirect bilirubin, Potassium, Creatinine, Total cholesterol, Chloride, Blood urea nitrogen, Low-density lipoprotein, Carbon dioxide, AST, High-density lipoprotein, Calcium, ALT, Triglycerides, Glucose, Alkaline phosphatase, Uric acid, Albumin, Lactate dehydrogenase, CPK. Visits include screening, Day 0, Day 7, Day 56.

Coagulation: Prothrombin time and partial thromboplastin time. Visits include screening, Day 0, Day 7, Day 56.

Urinalysis: Color, Glucose, Red blood cells, Clarity, Blood, Hyaline and other casts, pH, Bilirubin, Bacteria, Specific gravity, Leukocyte esterase, Epithelial cells, Ketones, Nitrite, Crystals, Protein, White blood cells, Yeast. Visits include screening, Day 0, Day 7, Day 56.

Serology: HIV-1/2 antibodies, HBsAg Hepatitis, C virus antibodies. Collecting at screening visit only.

Pregnancy: Serum pregnancy tests will be performed for females of reproductive potential at screening, after which urine pregnancy tests will be performed. Visits include screening, Day 0 and Day 56.

FSH: Follicle stimulating hormone testing will be performed at screening to confirm post-menopausal status in female participants who have had at least 12 months without menses. Collecting at screening visit only.

All observed and change from baseline results of hematology, biochemistry, and coagulation parameters data will be summarized by treatment group, at each scheduled visit using descriptive statistics (n, mean, SD, median, minimum, and maximum) for each scheduled study assessment for the Safety Analysis Set.

For urinalysis data, the continuous variables will be summarized by treatment group at each scheduled visit using descriptive statistics (n, mean, SD, median, minimum, and maximum).

Individual participant data listings of laboratory results will be presented. Values outside of the laboratory's reference range (i.e., those with low or high values) will be flagged in the listings.

The other laboratory tests: FSH, serology and serum pregnancy test will be listed.

12-Lead ECG

The 12-lead ECG will include the following measurements: Ventricular Rate, PR Interval, RR Interval, QRS Duration, QT Interval, QTcF Interval. And it will be summarized for the Safety Analysis Set.

Overall evaluation of safety ECGs will be summarized by treatment group, using frequency counts and percentage of participants as normal or abnormal, and the relevance of the abnormality will be summarized by clinically significant (CS) or not clinically significant (NCS).

Observed and change from baseline in ECG parameters will be summarized by treatment over each scheduled time-point/visit in terms of absolute values using descriptive statistics (n, mean, SD, median, minimum, and maximum).

Individual data listings of ECG results along with the Investigator-identified ECG abnormalities will be presented for each participant by treatment group.

Vital Signs

Vital signs (systolic and diastolic blood pressure, heart rate, respiratory rate, and temperature) will be summarized using the descriptive statistics for each vital sign measurement and change from baseline by treatment group, visit and timepoint using the Safety Analysis Set.

Vital Sign data will be listed by individual time course for each parameter.

Physical Examination

Physical examinations will include examination of the following body systems: head, eyes, ears, nose and throat (HEENT); cardiovascular, respiratory, gastrointestinal, dermatological, musculoskeletal, nervous systems, lymph nodes and general appearance.

The physical examination findings (normal, abnormal NCS, abnormal CS) will be summarized using counts and percentages by treatment group for each body system using the Safety Analysis Set.

All physical examination findings will also be listed individually for each participant by treatment.

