12.6.3. Recording Adverse Events

Adverse events spontaneously reported by the participant and/or in response to an open question from the study personnel or revealed by observation will be recorded during the study at the

investigational study center. Clinically significant changes in laboratory values, blood pressure, and pulse need not be reported as AEs. However, abnormal values that constitute an SAE or lead to discontinuation of administration of study treatment must be reported and recorded as an AE. Information about AEs will be collected from the signing of the consent form until 30 days following the last dose of study treatment. Serious AE information will be collected from signing of the consent form until 30 days following the last dose of study treatment. The AE term should be reported in standard medical terminology when possible. For each AE, the investigator will evaluate and report the onset (date and time), resolution (date and time), intensity, causality, action taken, serious outcome (if applicable), and whether or not it caused the participant to discontinue the study.

Intensity will be assessed according to the following scale:

- Mild (awareness of sign or symptom, but easily tolerated)
- Moderate (discomfort sufficient to cause interference with normal activities)
- Severe (incapacitating, with inability to perform normal activities)

It is important to distinguish between serious and severe AEs. Severity is a measure of intensity whereas seriousness is defined by the criteria under Section [12.6.1.2](#). An AE of severe intensity may not be considered serious.

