12.6.4. Reporting Adverse Events

All SAEs (related and unrelated) will be recorded from the signing of consent form until 30 days following the end of treatment exposure. Any SAEs considered possibly or probably related to the investigational product and discovered by the investigator at any time after the study should be reported. All SAEs must be reported to the sponsor within 24 hours of the first awareness of the event. The investigator must complete, sign, and date the SAE pages, verify the accuracy of the information recorded on the SAE pages with the corresponding source documents, and send to the sponsor.

Additional follow-up information, if required or available, should all be reported to the sponsor within 24 hours of receipt and this should be completed on a follow-up SAE form and placed with the original SAE information and kept with the appropriate section of the eCRF and/or study file.

The sponsor is responsible for notifying the relevant regulatory authorities of certain events. It is the Principal Investigator's responsibility to notify the Institutional Review Board (IRB) or Independent Ethics Committee (IEC) of all SAEs that occur at his or her study center. Investigators will also be notified of all unexpected, serious, drug-related events (7/15 Day Safety Reports) that occur during the clinical study. Each study center is responsible for notifying its IRB or IEC of these additional SAEs.

All AEs that lead to a participant's withdrawal from the study must be reported to the sponsor's medical monitor within 30 days.

Refer to the study manuals for procedures to be followed.

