15.3.3. Safety Analysis

All on-treatment safety data will be assessed descriptively for AEs, SAEs, clinical laboratory measurements, viral serology, vital signs, physical examinations, and ECGs. No formal statistical analysis will be performed on safety outcomes; inferences, if any, will be derived through clinical review and interpretation.

All TEAEs will be summarized overall and for each body system and preferred term by treatment group, relationship to investigational product, and severity. For tabulations by severity, only a participant's most severe event within the category (eg, overall, body system, or preferred term) will be counted. Adverse events will be dichotomized into "related" (definitely, probably, and possibly) and "unrelated" (unlikely and not related). "Treatment-emergent" will be defined as starting or worsening after the first dose of investigational product. If the start date is missing, the event is assumed to be treatment emergent. All SAEs will be tabulated.

Vital signs, including blood pressure, heart rate, body temperature, respiration rate, and weight will be summarized by treatment group at baseline and at each scheduled visit.

Clinical safety laboratory data will be summarized descriptively by treatment group at baseline and at subsequent scheduled visits. Summaries of safety laboratory parameters will include the first measurement of each scheduled assessment but repeat assessments done at the same study time point will not be included in summary calculations. Laboratory data will also be listed by treatment, participant, and visit. Listings will include scheduled, unscheduled, and repeat evaluations. A listing of markedly abnormal values, as defined in the SAP, will additionally be generated.

Abnormal physical examination findings that suggest a clinically significant worsening from baseline will be reported as AEs and analyzed as such. Clinically significant findings noted prior to start of investigational product treatment will be recorded as medical history and analyzed as such.

Concomitant medications will be tabulated by preferred term, and treatment group. For the purposes of data collection, a medication's usage will be considered concomitant if it was started within 14 days prior to informed consent and continued after administration of the investigational product. If the start date is missing, it will be assumed that the medication was used concomitantly.

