Visit	V-1	V0	V1	V2	V3	V4	V5	V6	
Week	-6	-	0	1	2	4	6	8	
Day	-	-	0	7	14	28	42	56	
Window	≤ 6 weeks	-	-	± 3 days	± 3 days	± 3 days	± 3 days	± 3 days	
DSQ compliance assessment	-	-	X	X	X	X	X	X	
Retrieval of DSQ handset	-	-	-	-	-	-	-	X	
Esophageal endoscopy and biopsy with EoE-EREFs	EGD	-	-	-	-	X		-	
EoEHSS - histology scoring	X	-	-	-	-	X		-	
PGI-S	-	-	X	-	X	X	X	X	
PGI-C	-	-	-	-	X	X	X	X	
Safety									
Physical examination	X	-	X	X	X	X	X	X	Predose on Day 0.
ECG	X	-	X	X	X	X	X	X	
Height	X	-	-	-	-	-	-	-	
Weight	X	-	X	X	X	X	X	X	
Vitals	X	-	X	X	X	X	X	X	Should be measured within 15 minutes prior to dosing, and +15 minutes (+/- 5 minutes) postdose on Days 0, 7, and 14.
Diet history	X	X	X	X	X	X	X	X	
Concomitant medications and procedures	X	X	X	X	X	X	X	X	
Review of adverse events	-	X	X	X	X	X	X	X	

Procedures	Screening Period	Prior to Rand	Rand/ Baseline	Treatment Period				End of Study/ Final Safety	Notes
				V2	V3	V4	V5		
Visit	V -1	V0	V1					V6	
Week	-6	-	0	1	2	4	6	8	
Day	-	-	0	7	14	28	42	56	
Window	≤ 6 weeks	-	-	± 3 days	± 3 days	± 3 days	± 3 days	± 3 days	
Local laboratory									
Hematology and serum chemistry	X	-	X	X	X	X	X	X	
Coagulation	X	-	X	X	X	X	X	X	Should be performed before the procedure of endoscopy with esophageal biopsies on days the procedure is performed.
Urinalysis	X	-	X	X	X	X	X	X	
Serology	X	-	-	-	-	-	-	-	
Pregnancy testing	X	-	X	-	-	-	-	X	Serum pregnancy test at screening; urine pregnancy test at all subsequent time points.
FSH testing	X	-	-	-	-	-	-	-	FSH of 2.25 U/mL must be documented to confirm post-menopausal status in female participants who have had at least 12 months without menses.
Research samples/ Central laboratory									
Blood PK sampling	-	-	X	X	X	X	X	X	Blood sample for PK concentrations collected predose on Day 0 only; 4min (+/- 1 min) postdose on Days 0, 7, and 14.
Antidrug antibodies	-	-	X	-	-	-	-	X	Predose on Day 0.

Procedures	Screening Period	Prior to Rand	Rand/ Baseline	Treatment Period				End of Study/ Final Safety	Notes
				V2	V3	V4	V5		
Visit	V-1	V0	V1	V2	V3	V4	V5	V6	
Week	-6	-	0	1	2	4	6	8	
Day	-	-	0	7	14	28	42	56	
Window	≤ 6 weeks	-	-	± 3 days	± 3 days	± 3 days	± 3 days	± 3 days	
Biopsies for central lab	X	-	-	-	-	X	-	-	Screening endoscopy with esophageal biopsies and photographs are to be performed during screening period to allow results to be available prior to Visit 1.
Central histology result received prior to visit	-	X	-	-	-	-	-	-	

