11 CHANGES TO ANALYSES SPECIFIED IN PROTOCOL

The below mentioned endpoints will not be analysed for this study.

Eosinophilic Esophagitis Diagnostic Panel (EDP) Transcriptome

RNA sequencing and EDP transcriptome will be evaluated. A molecular EDP has been identified that is composed of 94 EoE genes and distinguishes EoE from control individuals without esophagitis or with GERD ([Wen 2013](#)).

The EDP signature will be evaluated in biopsy samples. Using a method reported by ([Wen 2015](#)), the EoE transcriptome will be determined using the EDP from extracted RNA.

The Relative change will be provided for EDP transcriptome signature by treatment group.

Relative change = $\{(Post\ baseline\ value - Baseline\ value) / Baseline\ value\} * 100$.

Immune Cells and Markers of Inflammation

Immune cells and markers of inflammation include: immune cell phenotyping (T-subsets, B-subsets, and macrophage subsets); A20; serum cytokines; serum IgE/IgG4; and serum eosinophil derived neurotoxin (EDN) for eosinophil activation.

Relative change in immune cells and markers of inflammation pre- and post dose administration at baseline, and Weeks 1, 2, 4, 6, and 8 will be provided. Separate listing will be provided.

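### Two safety passages contradict the study's own schedule: the SAP 7.8 laboratory lists omit Days 14, 28 and 42, and the protocol's 30-day AE/SAE window closes before the Day 56 AE review

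*SAP*

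**What the plan says.** **Laboratory visits.** In SAP 7.8, under Clinical Laboratory Data, the hematology entry ends "Platelet count and differential (neutrophil, lymphocyte, monocyte, eosinophil, and basophil). Visits include screening, Day 0, Day 7, Day 56". The coagulation entry reads "Coagulation: Prothrombin time and partial thromboplastin time. Visits include screening, Day 0, Day 7, Day 56", and biochemistry and urinalysis carry the same four time points. SAP Table 1 (section 2.2) and protocol Table 3 mark the row "Hematology and serum chemistry", and the coagulation and urinalysis rows, at screening and at Days 0, 7, 14, 28, 42 and 56.

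Further on, SAP 7.8 says that "hematology, biochemistry, and coagulation parameters data will be summarized by treatment group, at each scheduled visit", and it has a similar sentence for urinalysis. Protocol 15.3.3 says: "Clinical safety laboratory data will be summarized descriptively by treatment group at baseline and at subsequent scheduled visits". SAP section 11, which records departures from the protocol, opens "The below mentioned endpoints will not be analysed for this study" and names only the EDP transcriptome and the immune-cell and inflammation markers.

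**Adverse events.** Protocol 12.6.3 states: "Information about AEs will be collected from the signing of the consent form until 30 days following the last dose of study treatment". Protocol 12.6.4 states: "All SAEs (related and unrelated) will be recorded from the signing of consent form until 30 days following the end of treatment exposure". Sections 12.6.1.1 and 12.6.1.2 use the same 30-day limit. Against this, the safety endpoint in protocol 6.4.2 and SAP 5.2 has participants monitor AEs up to their last study visit. Both schedules place an AE review at Day 56, and protocol 7.1 assesses safety through Week 8.

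**The concern.** Safety and tolerability is a secondary objective, and it will be judged only from by-arm descriptive summaries, with about 12 participants per arm (36 / 3). Which visits are tabulated and which events are recorded should not depend on the sentence a programmer or a site happens to read.

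A programmer working from the visit lists would produce laboratory tables with nothing between Day 7 and Day 56, so the only tabulated value after the third dose would come 42 days later. The panels concerned include neutrophils, platelets, transaminases and CPK, which protocol 8.3.2 and 8.3.3 use in decisions to stop or delay treatment. The SAP's precedence clause covers conflicts with the protocol. It does not settle this one, because the SAP disagrees with itself.

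For AEs, a site applying the 30-day rule and a site applying the last-visit rule would record different events late in follow-up. The difference is largest for participants who stop dosing early. Protocol 8.3.1 keeps them on the full visit schedule, while their 30 days run from an earlier last dose. Several of the stopping criteria in 8.3.2 are safety events.

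**Working it through.** The plan states no figure for either point, so the check compares the passages and counts days.

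**1. Laboratory visits**

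- Scheduled post-baseline visits (SAP Table 1, protocol Table 3): Days 7, 14, 28, 42, 56 = 5.
- Named in the SAP 7.8 lists: Days 7 and 56 = 2.
- Omitted: Days 14, 28 and 42, so 3/5 = 60%, the same in all four panels.
- Stretch without a tabulated value: 56 − 7 = 49 days. Third dose to next tabulated value: 56 − 14 = 42 days.
- If every scheduled visit is summarized instead: 0 of 5 omitted.

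The lists could be read as examples only. The pregnancy-test entry in the same section argues against that: it uses the same wording for screening, Day 0 and Day 56, which is exactly the complete schedule for that test.

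**2. AE and SAE window**

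Inputs: doses on Days 0, 7 and 14 (protocol 9.1); window end = last dose + 30 days (protocol 12.6.3, 12.6.4); final visit Day 56; ±3 days at Visits 2 to 6, so the final visit falls on Day 53 to 59.

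Gap = final visit day − (last dose day + 30).

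| Last dose received | Dose day (window) | Collection ends (window) | Nominal gap | Smallest to largest gap |
|---|---|---|---|---|
| Third | 14 (11–17) | 44 (41–47) | 56 − 44 = 12 days | 53 − 47 = 6 to 59 − 41 = 18 |
| Second | 7 (4–10) | 37 (34–40) | 56 − 37 = 19 days | 53 − 40 = 13 to 59 − 34 = 25 |
| First | 0 | 30 | 56 − 30 = 26 days | 53 − 30 = 23 to 59 − 30 = 29 |

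After a third dose on Day 14, the 30-day rule covers 30 / (56 − 14) = 30/42 = 71% of the remaining follow-up. No use of the visit windows closes the gap: the latest end of collection is Day 47 and the earliest final visit is Day 53.

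**The case against.** On the laboratory point, the visit lists sit in a description of the panels, while the analysis rule comes later and asks for every scheduled visit. The SAP schedule and protocol 15.3.3 agree with that rule, and SAP section 11 declares no change. All of this suggests a copying slip rather than a dropped analysis. Individual results are still listed and flagged against the reference range, and the mock tables, which are not available here, may already be right. That stands as far as intent goes, and 60% is the worse of two readings. But the same short list appears four times, and the text supports both readings.

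On AEs, the 30-day rule is stated consistently within protocol 12.6, and the last-visit sentence says what participants are asked to monitor, not when recording stops. Protocol 12.6.4 keeps possibly or probably related SAEs reportable at any time after the study. AESIs must be reported within 24 hours of identification. Physical examinations continue to Day 56, and protocol 15.3.3 has clinically significant worsening reported as an AE. The treatment-emergent definition has no end date, so late events would be tabulated if recorded.

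Most of this is fair and narrows the exposure to mainly non-serious AEs and unrelated SAEs. It does not remove the conflict. The 24-hour AESI rule sets the speed of reporting, not a longer collection period. An AE review at Day 56 also has no clear purpose if AE collection has already ended. The 19- and 26-day gaps apply only to participants who stop dosing early and stay on schedule, and the documents give no expected number of them.

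**Conclusion.** Both contradictions hold in the current text and should be fixed.

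- **Laboratory:** 3 of 5 post-baseline visits are lost from the by-arm tables if the SAP lists are followed, and none if the later sentence is followed.
- **AE/SAE collection:** it ends 12 days before the Day 56 review after all three doses (6 to 18 with windows), 19 days before if the second dose is the last (13 to 25), and 26 days before if the first is (23 to 29).

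The figures assume that visits and doses fall within the stated windows and that participants who stop dosing stay on the visit schedule. The effect on AE counts cannot be estimated, because the documents give no late event rate and no expected number of early stoppers. The primary endpoint and the efficacy summaries are not affected.

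**What to change.** 1. In SAP 7.8, replace the visit lists for hematology, biochemistry, coagulation and urinalysis with screening and Days 0, 7, 14, 28, 42 and 56, as in SAP Table 1.
2. Reconcile protocol 12.6.1.1, 12.6.1.2, 12.6.3 and 12.6.4 with the safety endpoint, so that AEs and SAEs are collected to the last study visit or to 30 days after the last dose, whichever is later. Leave the 12.6.4 provision on related SAEs found after the study unchanged. The SAP's treatment-emergent definition needs no edit.

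Cost: four lists in the SAP, and a small protocol amendment that goes to the IRB. No visits or samples are added, because the laboratory draws and the Day 56 AE review are already scheduled. If follow-up has already finished, events that were never recorded may not be recoverable. The clinical study report should then state which collection rule the sites applied.
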